Study protocol

Project title: Hysteroscopic evaluation of Fallopian tubal patency compared to laparoscopic chromopertubation: a prospective, randomized study on the "flow" and "Parryscope" techniques

Brief title: Hysteroscopic evaluation of Fallopian tubal patency

Participants:

Investigator:

Assoc.[name].Doz. [name]

Participating Doctors:

[name]

Assoc. [name]. Doz. [name] a.o.Univ. [name]. [name]

Participating Clinics:

Medical University of Vienna, Department of Obstetrics

and Gynecology, Clinical Division of Gynecologic

Endocrinology and Reproductive Medicine

[name]

[name]

[contact]

[contact]

Introduction and scientific background:

Hysteroscopy is an important tool in the evaluation of sterility. [1-5] It allows direct visualization of the uterine cavity and enables the diagnosis of numerous pathologies, including endometrial polyps, intracavitary myomas and also more rare diseases associated with sterility and infertility, such as Asherman-syndrome and anomalies of the uterus itself. Hysteroscopy shows high reliability and is considered the gold standard for intrauterine evaluation [1-6].

When performing hysteroscopy, experts often assess the patency of the tubes via the visibility of flow of the hysteroscopic fluid going through the ostia of the tubes. In the recently published study "Assessment of tubal patency: A prospective comparison of diagnostic hysteroscopy and laparoscopic chromopertubation" it was demonstrated that visualizing contrasting substances disperse through the ostia is a significant and meaningful metric for tubal patency (sensitivity 85.2, 95% CI: 76.1-91.9; specificity: 66.1, 95% CI: 52.2-78.2). This confirmed the value of this approach, consistent with our previous retrospective study on the same topic [7]. Nevertheless, it is important to mention that the prospective study showed both a lower specificity (66.1% vs. 77.6%) and a lower positive predictive value (79.8% vs. 91.3%).

Pre- and posthysteroscopic vaginal sonography for the evaluation of the hysteroscopic fluid in the pouch of Douglas [9,10], selective hysteroscopic pertubation of the tubes [11] and the visibility of air bubbles traversing through the Fallopian tube ostia after an air infusion into the uterine cavity [10,12] have been reported to be reliable methods for hysteroscopic tubal patency assessment. Particularly the last one, also called the "Parryscope technique", named after its inventor, seems to be highly reliable, easy to conduct and clinically relevant [8,10,12]. The "Parryscope technique" reaches a sensitivity of min. 98.3% and a specificity of 83.7% [9] and, thus, seems to perform even better than the technique evaluating the "tubal flow".

Assessing tubal patency during hysteroscopy is highly relevant, particularly when it allows for a low cost, fast, gentle, and accurate way of gathering information that may guide clinical care. Therefore, it is important to know which of the above-mentioned techniques is the best. This prospective randomized study aims to compare the hysteroscopic assessment of the tubes via "tubal flow" [7] and the "Parryscope technique" [10,12]. At our department, the Clinical Division of Gynecological Endocrinology and Reproductive Medicine of the Medical University of Vienna, a diagnostic hysteroscopy is usually performed directly before every infertility-related laparoscopy. These operations are always performed by an expert in the field of reproductive surgery, which should guarantee a good clinical quality of our data set.

Study aims:

The primary aim of this study is to evaluate the relalibility of (1.) the hysteroscopic visualization of a "tubal flow" and (2.) the "Parryscope technique" as compared to the gold standard, namely laparoscopic chromopertubation.

Study hypothesis:

Null hypothesis: The hysteroscopically visualizable "tubal flow" and the "Parryscope technique" are similarly reliable in the evaluation of tubal patency.

Alternative hypothesis: The hysteroscopically visualizable "tubal flow" shows a lower sensitivity and specificity than the "Parryscope technique" for the evaluation of tubal patency.

Study design:

Prospective, randomized study.

Participants:

Inclusion criteria:

- The patient is subfertile, defined as being unable to become pregnant within a year despite unprotected sexual intercourse. It is also within the standard of care to be presumed subfertile if one has tried for six months and has known risk factors that would hinder conception, including but not limited to anovulation and endometriosis.
- A concurrent diagnostic hysteroscopy and laparoscopy with chromopertubation are performed at the Clinical Division of Gynecological Endocrinology and Reproductive Medicine at the Medical University of Vienna.
- The patient has given her written informed consent after detailed information on the study by medical professionals at the Department of Obstetrics and Gynecology of the Medical University of Vienna.
- The patient is ≥18 and ≤45 years old.

Exclusion criteria:

- The patient had a tubectomy on one or both sides.
- There is no "informed consent".
- The patients has active vaginal infection or other conditions that would preclude hysteroscopy.

Primary Outcome Parameters:

Hysteroscopic evaluation of tubal patency (either by a positive "tubal flow" or a visible flow of air bubbles in the "Parryscope technique") and the result of the laparoscopic chromopertubation (tubal patency existing or not existing).

Secondary Outcome Parameters:

For the descriptive analysis, several hysteroscopically visualizable additional parameters will be evaluated: (i) existence of any hysteroscopic abnormalities (including endometrial polyps, myomas, adhesions, anomalies or cervical stenosis). (ii) characteristics of the tubal "flow" – clearly visualizable or questionable, visualization of air bubbles and/or floating structures in the cavity. (iii) clarity of the hysteroscopic view (clear versus hazy).

Recruitment:

Women will be invited to participate by medical professionals at the Department of Obstetrics and Gynecology of the Medical University of Vienna using the above-mentioned criteria in the course of their admission to the ward one day before surgery. Potential participants are informed about the procedure, clinical relevance and the balance of risk and benefits incurred through study participation. Patients willing to participate will express this through written affirmation (a "consent form").

Parameters obtained:

The following parameters will be collected and included in the database. They do not require additional effort on behalf of the patients. All data will be obtained using the study-specific case report form and will be entered into a SPSS database in a semi-anonymized manner.

- Patient's age
- Body mass index
- Primary/secondary subfertility
- Obstetrical history (gravidity, parity)
- History of risk factors relating to tubal disease (chlamydia infection, endometriosis, etc.)
- Detailed information about the indication for surgery
- Main outcome parameter 1: Hysteroscopic findings: tubal patency assumed or not assumed in right/left tubal ostium (information provided separately for each side)
- Additional findings: any hysteroscopic abnormalities (including endometrium polyps, myomas, adhesions, anomalies or cervical stenosis). In the "tubal flow" group an additional finding would also be the presence of air bubbles. Moreover, the clarity of the hysteroscopic view will be evaluated (clear versus hazy).
- Duration of the hysteroscopic evaluation of tubal patency (in minutes).
- Additional interventions: Curettage and operative hysteroscopy.
- Uterine length.
- *Main outcome parameter 2*: Laparoscopic findings: tubal patency as assessed by chromopertubation (information provided separately for each side)
- Amount of blue dye used in chromopertubation
- Performance of any additional laparoscopic interventions during the operation
- A subjective assessment of pressure used in demonstrating patency with chromopertubation (low vs high, which affects accuracy and prognosis)

The additional data acquisition will be conducted to give an exact characterization of the patient population to allow a comparison with the published literature.

Techniques of hysteroscopic evaluation of tubal patency:

"Tubal flow"-group: a positive "flow" is defined as the observation of saline directly traversing the ostia, endometrial structures floating toward the ostia, or air bubbles traversing the ostia.

"Parryscope"-group: A small amount of air is introduced into the iv tubing by inverting the drip chamber to create air bubbles. When air enters the uterine cavity, a single large air bubble or stream of air bubbles traversing the ostia is considered indicative of tubal patency. At least 10 seconds of intracavitary evaluation is typically performed before air bubble entry to allow pressure equilibration if a hydrosalpinx is present [10]. At least 30 seconds of observation per ostia is performed if patency is not observed.

Additional considerations:

- 1. Since in the "flow"-group air bubbles might develop spontaneously and, thus, should be assessed, conducting the "Parryscope"-technique is only possible after the evaluation of the tubal flow
- 2. Reactive tubal spasms could occur especially during a prolonged hysteroscopy.
- 3. This is why in one particular patient only one technique should be performed.

Sample size calculation:

The calculation is based upon the following considerations:

- Direct comparison of the two groups is not possible. Hence, separate evaluation of the two
 methods will be performed. Evaluating both methods in one particular patient in the course
 of a single intervention is impossible without a mutual interference (see: "Additional
 considerations" above).
- 2. The "flow effect" is considered the less reliable method and thus, the sample size was aligned to this method. An odds ratio of approximately 10, an alpha of 5%, a power of 80%, a general disease likelihood of 39% and a sensitivity of 66% for occluded tubes result in a total amount of 59 tubes and, accordingly, 30 patients.
- 3. Thus, the group for the "Parryscope"-technique should also contain 59 tubes (= 30 patients).
- 4. The randomization of the total 60 patients is performed as block randomization in 4 blocks via the software "R".

Statistical analysis:

Numerical data (age, body mass index) will be reported as mean and standard deviations, nominal variables (primary/secondary sterility, indication for the reproductive medical intervention, visibility of the "flow" in the left and right tubal ostium, pathologies in the uterine cavity in the hysteroscopy, patency of the tubes via chromopertubation, information about further laparoscopic interventions during the operation) as number and frequency. The McNemar Test will be used for the calculation of the reliability of the hysteroscopic assessment of the tubes. The sensitivity, specificity, positive and negative predictive values will be provided including the according 95% confidence intervals (95% CI) for both study groups (evaluated technique versus gold standard laparoscopic chromopertubation). The according odds ratio is over 10 will be evaluated by the use of a binary logistic regression model. Statistical analyses were performed with the software "R". Differences were considered significant if p<0.05.

Data quality evaluation:

Extreme values will be double-checked. In addition, random checks by two independent investigators will be conducted to ensure the accuracy of our data.

Risk-benefit-analysis:

In this prospective study, no further data acquisitions, follow-up examinations or surveys will be necessary. Except from the above-mentioned additional findings during the interventions, the only additional data to be collected would already be inherently obtained as part of procreative evaluation. Accordingly, if patients would be undergoing the described interventions (hysteroscopy, laparoscopy) independent of their choice to participate, this should not shift cost or risk for them. Additionally, since the study evaluations are minimal risk (visual observation of natural intracavitary flow patterns and deliberate addition of 0.5 mL of air in to saline during hysteroscopy (where greater amounts routinely enter the uterus accidentally through how lines are primed), safety should remain high. The analysis and publication of the data will be done with patient deidentification.

Agreement on the access of the principle investigator:

The principle investigator will have access to all study documents and statistics at all times.

References:

- 1. CHOLKERI-SINGH, A. & SASAKI, K. J. 2015. Hysteroscopy for infertile women: a review. J Minim Invasive Gynecol, 22, 353-62.

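### The comparative hypotheses are not complementary and have no between-arm analysis; if both measures had to differ significantly, support would be unlikely even at the protocol's own figures

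*Combined protocol and SAP*

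**What the plan says.** The Study hypothesis section sets a null under which the two techniques "are similarly reliable in the evaluation of tubal patency". The alternative is that flow "shows a lower sensitivity and specificity than" the Parryscope technique. No metric or margin defines similar reliability.

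The figures behind this expectation are in the introduction. For flow it gives "sensitivity 85.2, 95% CI: 76.1-91.9; specificity: 66.1, 95% CI: 52.2-78.2", from a prospective study; a retrospective study is cited with a specificity of 77.6%. The Parryscope technique "reaches a sensitivity of min. 98.3% and a specificity of 83.7" per cent.

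The Sample size calculation section says the two groups cannot be compared directly and that each method will be evaluated separately. It sizes the flow arm on "An odds ratio of approximately 10, an alpha of 5%, a power of 80" per cent, with "a general disease likelihood of 39% and a sensitivity of 66% for occluded tubes". The result is 59 tubes (30 patients), and the Parryscope arm is set equal.

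The Statistical analysis section plans a McNemar test, accuracy measures with 95% CIs and a logistic odds ratio, each technique against chromopertubation. Significance is p<0.05, with sidedness not stated.

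**The concern.** There are two separate problems of form.

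- **The hypotheses leave a gap.** Flow could be worse on sensitivity and equal or better on specificity, or the reverse. Such a result is plausible for two diagnostic techniques, and it fits neither the null nor the alternative.
- **The hypothesis is comparative and the analysis is not.** Women are randomised between techniques and the introduction wants to know which is best, yet nothing in the analysis sets one arm against the other.

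The obvious repair, adding a between-arm test under the present wording, brings a further difficulty. Read literally, the alternative then needs two significant differences at once, one among patent tubes and one among occluded tubes. Missing either would leave a null of similar reliability unrejected, and a reader could take that as a finding of similarity. The wording and the analysis therefore need to change together.

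**Working it through.** **The plan's own figure.** An odds ratio of 10 with 66% detection of occluded tubes implies 16.3% false occluded calls: odds 0.66/0.34 = 1.941, divided by 10 = 0.194, and 0.194/1.194 = 0.163. Standard formulas on that direct reading (two proportions, logistic regression, Wald log odds ratio; 80% power) give 23–38 tubes, not 59. One other mapping gives 61 (66% as the baseline event rate, 39% as the exposed share, two-sided logistic formula), but the protocol does not describe it. Either way the 59 is a within-arm size, and the protocol states no between-arm power to reproduce.

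**Inputs.** Occluded tubes per arm: 59 × 0.39 = 23. Patent tubes per arm: 59 × 0.61 = 36. Reading 39% as the occluded share fits the prior flow study: PPV = 0.61 × 0.852 / (0.61 × 0.852 + 0.39 × 0.339) = 79.7%, against the 79.8% quoted in the introduction. I take a positive result to mean patent for both techniques; the protocol does not say so for Parryscope. Tubes are treated as independent at first.

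**Each difference alone, two-sided 5%.** Wald power = Φ(d/SE − 1.96).

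- Sensitivity: d = 0.983 − 0.852 = 0.131; SE = √(0.852 × 0.148/36 + 0.983 × 0.017/36) = 0.0630; power Φ(0.12) = 54.8%.
- Specificity: d = 0.837 − 0.661 = 0.176; SE = √(0.661 × 0.339/23 + 0.837 × 0.163/23) = 0.1252; power Φ(−0.55) = 29.0%.

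**Both differences together.** The two tests use different tubes, so the joint power is the product.

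| Test | Sensitivity | Specificity | Joint |
|---|---|---|---|
| Fisher, two-sided | 30.0% | 19.3% | 5.8% |
| Wald, two-sided | 54.8% | 29.0% | 15.9% |
| Chi-square, two-sided | 59.8% | 28.3% | 16.9% |
| Fisher, one-sided | 45.1% | 28.3% | 12.7% |
| Wald, one-sided | 66.8% | 40.5% | 27.1% |
| Chi-square, one-sided | 73.7% | 39.1% | 28.8% |

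That is about 6–17% two-sided and 13–29% one-sided. Simulation with random numbers of occluded tubes stays inside these ranges.

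**Sensitivity of the result.**

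- Flow specificity 77.6% instead of 66.1%: joint power 1–5% two-sided, 3–10% one-sided.
- Occluded and patent shares swapped: 6–15% two-sided, 9–28% one-sided.
- Tubes correlated within a woman (assumed ICC 0.2–0.5): by the pooled normal approximation, 14.5% falls to 11–7% two-sided and 25% falls to 20–15% one-sided.
- Joint power of 80% would need about 248 tubes per arm two-sided or 198 one-sided, tubes independent.

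**What estimation would deliver.** The 95% half-widths are 1.96 × 0.0630 = 12.3 points for sensitivity and 1.96 × 0.1252 = 24.5 points for specificity. If both tubes of each woman share the same patency status and the ICC is 0.2–0.5, multiplying by √(1 + ICC) gives 13.5–15.1 and 26.9–30.1 points.

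**The case against.** The strongest reply is that these powers belong to a test the plan never schedules. The primary aim is each technique against chromopertubation, and the analysis follows that aim. The joint rule is also an inference: naming sensitivity and specificity together may only list the two measures expected to be lower, and both will be reported separately in each arm, so a one-sided advantage would be visible. This stands. The percentages are conditional, and they are not the power of the trial as planned.

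Three stronger readings are tempting and are not supported.

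- **That the gap between null and alternative lowers the power.** It changes no rejection probability. The joint requirement does, and so does the number of tubes: specificity alone, with no joint requirement, has only 19–29% power two-sided on about 23 occluded tubes per arm.
- **That the plan would conclude similarity from a non-significant result.** No section contains such a rule. The wording leaves room for that reading and does not prescribe it.
- **That one combined test is needed.** A two-sided test of sensitivity plus specificity (difference 13.1 + 17.6 = 30.7 points, SE 14.0) has about 59% Wald power, or 31% at a flow specificity of 77.6%. It would also label equal and opposite differences as no difference, which hides the very case the present hypotheses leave out.

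The reply does not remove the mismatch itself. The protocol states a comparative hypothesis and randomises women to test it, then analyses each arm alone. Its reason for ruling out direct comparison, that the techniques interfere with each other, applies within one patient and not between randomised arms.

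**Conclusion.** The point holds in a limited form. The hypotheses are not complementary, similar reliability is undefined, and no planned analysis addresses the comparison. This follows from the text and rests on no calculation.

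The size is conditional. If a between-arm test were added and both differences had to be significant, support for the alternative would be about 6–17% with two-sided 5% tests and 13–29% with one-sided ones. This assumes that the introduction's accuracy figures are true and share one orientation, 36 patent and 23 occluded tubes per arm, and independent tubes. Sidedness is my assumption, as the protocol gives only p<0.05 and its alternative is directional. Every variant checked is far below 80%.

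**What to change.** 1. **Study hypothesis.** State two pairs, one for sensitivity and one for specificity, each as no difference versus a difference between techniques. Define a positive result (patent) once for both. The expected direction can stay as background.
2. **Statistical analysis.** Add the between-arm difference in each measure with a 95% CI that allows for two tubes per woman, each interpreted on its own. Say that a non-significant difference is not evidence of similar reliability. Name the interval method in advance: at 98.3% on 36 tubes, the chance of no missed patent tube in the Parryscope arm is 0.983^36, about 54% with independent tubes, and a simple Wald interval behaves badly there. A score-type interval adjusted for clustering is one option.
3. **Sample size calculation.** Reconcile the statement on direct comparison with the randomised design: comparison is ruled out within a patient and is possible between arms. Say that the between-arm comparison is estimation without 80% power.

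A single test of sensitivity plus specificity is optional.

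The cost is rewording in three sections and a short added analysis, with no extra patients or data. The downside is imprecision: about ±12 points for sensitivity and ±25 for specificity, wider if tubes within a woman are correlated. The trial may therefore not settle which technique is better.

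### The only stated hypothesis is that tubal flow is less accurate than the Parryscope technique, but the plan rules out comparing the groups and specifies no between-arm analysis

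*Combined protocol and SAP*

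**What the plan says.** The comparative side is in the Introduction and scientific background and in the Study hypothesis:

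- The introduction says "it is important to know which of the above-mentioned techniques is the best" and "This prospective randomized study aims to compare the hysteroscopic assessment of the tubes" by the two methods.
- The null hypothesis is that the techniques "are similarly reliable in the evaluation of tubal patency". The alternative is that tubal flow "shows a lower sensitivity and specificity than the 'Parryscope technique' for the evaluation of tubal patency".

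The non-comparative side is in three other places:

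- Study aims: the primary aim is the reliability of each technique "as compared to the gold standard, namely laparoscopic chromopertubation".
- Sample size calculation, consideration 1: "Direct comparison of the two groups is not possible. Hence, separate evaluation of the two" methods follows. The supporting sentence begins "Evaluating both methods in one particular patient in the course" of one intervention, and says this cannot be done without mutual interference. Consideration 2 sizes the flow arm alone: an odds ratio of about 10, alpha 5%, power 80%, 39% disease likelihood and "a sensitivity of 66% for occluded tubes result in a total amount of 59 tubes". Consideration 3 gives the Parryscope arm the same size.
- Statistical analysis: a McNemar test, accuracy measures with 95% confidence intervals for each group against chromopertubation, and a logistic regression concerning an odds ratio over 10. No difference, ratio, test or interaction between the arms is named.

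**The concern.** A hypothesis about a difference between two techniques needs an estimate of that difference. The plan yields two separate accuracy tables. A comparative conclusion could then come only from viewing two sets of intervals side by side, or from one arm reaching significance and the other not. Neither estimates the difference, and any contrast chosen once the data are seen would be post hoc.

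The reason given for not comparing does not support the statement. If two techniques interfere within a patient, a paired comparison is lost. That is a good reason to randomise patients to one technique each, which the trial does, and randomised arms are what make an unpaired comparison valid.

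**Working it through.** **1. Does any planned analysis compare the arms?**

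- *McNemar test.* It needs paired results. Each patient gets one technique, so the only available pair is hysteroscopy and chromopertubation on the same tube. The test then asks whether those two give equal patency rates within an arm.
- *Accuracy tables.* They are defined as technique against reference, separately by group.
- *Logistic regression.* It is tied to the odds ratio over 10, which is the sizing input for the flow arm. No arm term or arm-by-reference interaction is given.
- *The p<0.05 sentence.* It names no contrast.

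**2. What does the 59-tube figure power?** With the inputs as labelled, 66% of occluded tubes are called occluded. The odds are 0.66/0.34 = 1.94; divided by 10 this is 0.194, a rate of 16.3% in patent tubes. Two-sided at 80% power, a two-proportion formula gives 31 tubes (39 with continuity correction), a logistic formula for a binary covariate 29, and a Wald log-odds-ratio formula 35. The logistic formula comes near 59 (60.8 tubes) only if 66% is read as a reference rate rising to 95.1%, which does not fit its label. In every version the calculation is within one arm; no flow-versus-Parryscope difference enters.

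**3. What could a between-arm comparison deliver at this size?**

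Inputs from the documents:
- 59 tubes per arm and 39% occluded give 59 × 0.39 = 23 occluded and 59 × 0.61 = 36 patent tubes per arm.
- Flow (introduction): sensitivity 85.2%, specificity 66.1%. These match 75/88 and 37/56, whose exact 95% intervals are 76.1–91.9 and 52.2–78.2, as printed; 56/144 = 38.9% are occluded. A positive result therefore means patent, and the 66% called sensitivity for occluded tubes in the sizing is the introduction's specificity.
- Parryscope (introduction): sensitivity at least 98.3%, specificity 83.7%. The meaning of positive is not stated.

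Power by exact enumeration of two binomials, counting rejections in the hypothesised direction, tubes independent. Ranges run from Fisher's test to the uncorrected chi-square.

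| Contrast (positive = patent) | Two-sided 5% | One-sided 5% |
|---|---|---|
| Occluded tubes, 66.1% vs 83.7% (23 per arm) | 19–28% | 28–39% |
| Patent tubes, 85.2% vs 98.3% (36 per arm) | 30–60% | 45–74% |
| Both (product) | 6–17% | 13–29% |

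Two tubes from one patient are unlikely to be independent. In simulated trials with a patient-level permutation test, as the assumed within-patient correlation rises from 0 to 0.5, two-sided power falls from 27% to 20% (occluded), 54% to 42% (patent) and 15% to 9% (both). Expected 95% half-widths with a cluster-adjusted score interval are about 24–27 points (occluded) and 15–17 points (patent).

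If the Parryscope figures instead treat occluded as positive, occluded-tube power (66.1% vs 98.3%) is 84–91% two-sided. Patent-tube accuracy is then 85.2% for flow against 83.7% for Parryscope, which runs against the alternative.

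**4. Size needed for 80% power** (positive = patent, two-sided, independent tubes):

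n per arm = [1.96√(2p̄(1−p̄)) + 0.842√(p₁(1−p₁) + p₂(1−p₂))]² / (p₁ − p₂)²

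- Occluded: p̄ = 0.749; (1.202 + 0.505)² / 0.176² = 94.1, so 95 tubes; 94.1/(2 × 0.39) = about 121 patients.
- Patent: p̄ = 0.9175; (0.763 + 0.318)² / 0.131² = 68.05, so 69 tubes; 68.05/(2 × 0.61) = about 56 patients.
- Both: 124 patients per arm (component powers 0.81 × 0.99 = 0.80), or 99 one-sided, against 30 planned.

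**The case against.** The strongest reply is that the primary aim is intact. It asks how each technique performs against chromopertubation, and the sizing and per-group tables answer that. A few sentences changed in the introduction and hypothesis would remove the conflict without touching data or analysis. This is right as far as it goes, but the only formal hypothesis still has no analysis, and without a comparison the purpose of randomising is unexplained.

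Second, the plan never attaches its 80% power to a comparison; it says the size was aligned to the flow method. A reader who misapplies it does so against the text. That is fair, and this harm is secondary.

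Third, the Parryscope inputs are uncertain. The 98.3% is given as a minimum, so under positive = patent the patent-tube power is a floor and the patient numbers for that contrast and for both are upper values. The reference number attached to these figures leads, in the reference list, to a study of transvaginal sonography after hysteroscopy. The coding is assumed, and the correlation range has no basis in the documents. All this stands, and it limits the power figures to illustration. The finding itself needs none of them.

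Fourth, the logistic sentence is garbled, so an arm term is unspecified rather than excluded. That does not supply one.

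**Conclusion.** The concern holds, and the plan is wrong as written. It states that the groups cannot be compared for a reason that covers only comparison within a patient, and so leaves its directional between-technique hypothesis without an estimate or a test. The conflict is between the hypothesis and stated purpose on one side and the aim, sizing and analysis on the other; the design itself permits the comparison.

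How well 60 patients could answer the question depends on assumptions: 39% occlusion in both arms, the coding of the Parryscope figures, and the within-patient correlation. With patent as positive, support for the full two-part alternative is improbable (6–17% two-sided). With the opposite coding, the document's own figures contradict half of the alternative.

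**What to change.** Adopt one of two remedies before the data are analysed.

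**A (preferred, because the data are already being collected).**
- In the Sample size calculation, state that a within-patient comparison is not possible, in place of the statement about the groups. Say that the 80% power does not apply to the between-arm comparison.
- In the Statistical analysis, keep the within-arm tables for the primary aim. Add, for the hypothesis, the unpaired difference (flow minus Parryscope) with a 95% interval in (a) occluded tubes called occluded and (b) patent tubes called patent.
- Allow for two tubes per patient. One workable choice is a Newcombe score interval on cluster-adjusted effective tube numbers, using the other arm's design effect if one arm has no errors, with a test that permutes arm labels by patient. Say which governs if they disagree. An ordinary logistic arm effect would often not be finite: the chance of no Parryscope errors in 36 patent tubes is 0.983³⁶ = 54%.
- State whether tests are one- or two-sided, that the alternative is supported only if both contrasts favour Parryscope at 5% each, and that a non-significant result does not establish similar reliability.
- Use one definition of a positive result throughout.
- Label the comparison as estimation with limited power unless the trial is enlarged.

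Cost: about a paragraph, a little extra analysis and a less favourable power statement, with no extra patients. Powering both contrasts would take roughly four times the patients (124/30 = 4.1) if positive means patent. Under the opposite coding, no enlargement would support the two-part alternative at those figures.

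**B.** If no comparison is wanted, rewrite the hypothesis and purpose as within-arm accuracy and draw no comparative conclusion. Cost: a few sentences, and the answer to which technique is better.

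### The single 80% power figure is for an odds ratio of about 10 and does not cover the McNemar test assigned to reliability, which at 59 tubes has about 4–10% power (flow) or 11–31% (Parryscope)

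*Combined protocol and SAP*

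**What the plan says.** - **Study aims.** The primary aim is the reliability of each technique "as compared to the gold standard, namely laparoscopic chromopertubation".
- **Sample size calculation, consideration 2.** The inputs are "An odds ratio of approximately 10, an alpha of 5%, a power of 80%, a general disease likelihood of 39" per cent, and "a sensitivity of 66% for occluded tubes result in a total amount of 59 tubes and, accordingly, 30 patients". Consideration 3 gives the Parryscope group the same size. No formula, test, null value or sidedness is named.
- **Statistical analysis.** "The McNemar Test will be used for the calculation of the reliability of the hysteroscopic assessment of the tubes". Sensitivity, specificity and predictive values with 95% CIs follow for both groups. Then: "The according odds ratio is over 10 will be evaluated by the use of a binary logistic regression model". No analysis is labelled primary.
- **Introduction and scientific background.** Accuracy for flow is given as "sensitivity 85.2, 95% CI: 76.1-91.9; specificity: 66.1, 95% CI: 52.2-78.2", with patency as the positive result. The Parryscope technique "reaches a sensitivity of min. 98.3% and a specificity of 83.7" per cent.

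**The concern.** The plan states one power and one effect size, and the only test it ties to the word used in the primary aim is McNemar. A reader can easily take the 80% as covering that test.

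The two quantities differ in kind. A diagnostic odds ratio of 10 says that the hysteroscopic call depends strongly on the true state of the tube. McNemar ignores the concordant tubes and asks whether occluded tubes called patent are as frequent as patent tubes called occluded. A technique can have a high diagnostic odds ratio and many errors, and still give a null McNemar result because its errors are roughly balanced.

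The conclusion for each arm is at stake. If a non-significant McNemar result is set beside a stated 80% power, it could be taken as evidence that hysteroscopy agrees with chromopertubation. At this sample size it would carry almost no information.

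**Working it through.** **Inputs.** Occlusion 39%, sensitivity for occluded tubes 66%, odds ratio 10 and 59 tubes (Sample size calculation). Flow 85.2%/66.1% and Parryscope 98.3%/83.7% (Introduction). Assumptions: two-sided 5%, tubes independent, and 39% occlusion in both arms. As a check that 39% is the occlusion rate, PPV = 0.61×0.852 / (0.61×0.852 + 0.39×0.339) = 0.797, against the 79.8% that the Introduction reports for the prospective study.

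**Step 1: where the odds ratio comes from.** The flow figures give (0.852×0.661)/(0.148×0.339) = 11.2. The planning value of about 10 is therefore an association measure.

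**Step 2: can 59 be reproduced?** The Wald sample size for a log odds ratio with a binary covariate is n = (1.960+0.842)² × [1/((1−B)P1(1−P1)) + 1/(B·P2(1−P2))] / (ln OR)².
- *Plain reading.* B = 0.39 occluded and P2 = 0.66. The odds at 66% are 1.94, so an odds ratio of 10 gives P1 = 0.194/1.194 = 0.163. The bracket is 23.47, and n = 7.85×23.47/5.30 = 34.7, which is 35 tubes and not 59. With 23 occluded and 36 patent tubes, Fisher's test has about 97% power.
- *Unusual assignment.* Taking 66% as covariate prevalence and 61% as baseline gives P2 = 0.940, bracket 39.19 and n = 58.01, rounded up to 59.
- *McNemar route.* Entering 10 as the ratio of discordant tubes, with the discordant share cut to 0.146, gives 8.9/0.146, about 61 tubes; a ratio of 11.2 gives 58.

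Each near-match needs an input used in a way the text does not describe, so the formula cannot be identified.

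**Step 3: McNemar cells.**
- *Flow, sample size inputs:* occluded called patent 0.39×0.34 = 0.133 (7.8 tubes); patent called occluded 0.61×0.163 = 0.099 (5.9 tubes); ratio 1.34.
- *Flow, Introduction figures:* 0.39×0.339 = 0.132 (7.8 tubes); 0.61×0.148 = 0.090 (5.3 tubes); ratio 1.46.
- *Parryscope:* 0.39×0.163 = 0.064 (3.8 tubes); 0.61×0.017 = 0.010 (0.6 tubes); ratio about 6.1.

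The expected number of misclassified flow tubes is 7.8 + 5.3 to 7.8 + 5.9, about 13 to 14 of 59.

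**Step 4: McNemar power at 59 tubes.** This sums over the number of discordant tubes (binomial, n = 59) and their split between the two error types.

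| Scenario | Exact | Continuity-corrected | Uncorrected |
|---|---|---|---|
| Flow, sample size inputs | 4.8% | 4.3% | 7.6% |
| Flow, Introduction figures | 6.1% | 5.7% | 9.5% |
| Parryscope | 10.7% | 10.7% | 31.3% |

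For scale only, the unconditional formula [1.960√(sum) + 0.842√(sum − diff²)]²/diff², where sum and diff are the sum and difference of the two cells, gives 80% McNemar power at about 990 to 1,625 tubes for flow and about 200 for Parryscope. These are not proposed as targets.

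**The case against.** The strongest reply is that the odds ratio already has its own analysis. The plan evaluates it by logistic regression and nowhere says that the 80% belongs to McNemar. This stands: the power statement is not without a matching analysis, and the defect is that the plan does not say which analysis the 80% covers.

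A reader might infer several stronger things, and the documents do not support them.

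- *That 59 was miscalculated, or that the wrong kind of odds ratio was put into a McNemar formula.* No formula is given, and the near-matches come from different methods with reassigned inputs. This is conjecture.
- *That the 80% must be for an odds ratio tested against 1.* On the plain reading that power is about 97%. The text also speaks of an odds ratio over 10. If 10 were the null value, simulated power at a true odds ratio of 10 would be only about 5%.
- *That 59 tubes are too few to assess accuracy.* Low McNemar power when errors nearly balance reflects a near-null effect for that test. It says nothing about how well sensitivity and specificity are estimated.
- *That the flow figures hold for both arms.* In the Parryscope arm the ratio and the power are higher, though the power is still far below 80%.

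It is also fair to say that the plan does not announce that a null McNemar result will be read as agreement, and that the planned accuracy estimates would make the misclassified tubes visible. That limits the harm. It does not remove it, because McNemar is the test named for reliability and results are judged at p<0.05.

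**Conclusion.** The concern holds in a limited form: the stated 80% does not cover the test assigned to reliability. At 59 tubes McNemar has about 4–10% power in the flow arm and about 11–31% in the Parryscope arm, depending on the test version. A null result is expected in about 90% or more of flow-arm trials while about 13 of 59 tubes are misclassified, so it cannot be evidence of reliability.

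The figures rest on the protocol's planning values, two-sided 5% (sidedness is not stated), 39% occlusion in both arms and independent tubes, although most patients contribute two. The conclusion does not depend on recovering the sponsor's formula, because no McNemar version comes near 80% in either arm. This is a mismatch between the power statement and the analysis plan; no printed figure is shown to be miscalculated.

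**What to change.** - **Sample size calculation, consideration 2.** State which analysis and which null value the 80% refers to, taken from the calculation actually performed. State that it does not cover McNemar, and give McNemar power at 59 tubes as about 4–10% (flow) and 11–31% (Parryscope) at the planning figures. Do not write that the 80% is for an odds ratio tested against 1 unless the sponsor's calculation shows this.
- **Statistical analysis.** State that the reliability conclusion in each arm rests on sensitivity and specificity with their 95% CIs. Describe McNemar as a supportive check of whether the two error types balance, and say that its non-significance is not evidence of reliability or agreement.

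The cost is wording in two sections. No patients, procedures or data items are added. The downside is a less favourable power statement.
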